
Graduate Committee Chair/Faculty Advisor Name: _____

Department: _____

College: _____

Mailing Address (if not PVAMU): _____

Phone: _____

Fax: _____

E-mail: _____

Project Title:

Guided group telehealth to deliver evidence-based therapeutic care to Black college students

Anticipated Start and End Dates: 8/2024-8/2028

Funding Status:

Externally Funded* Grant Application* Internally Funded* Not Funded

Other _____

Funding Agency (if applicable):

NIH

**Must include a draft of the grant application. Once grant is completed/submitted, a final draft must be submitted to the IRB.*

Does this protocol require approval from multiple IRBs?

Yes, please state below

No, only from PVAMU IRB

PURPOSE OF STUDY

Provide a **brief** statement, in lay terminology, outlining the purposes of this study. The following issues must be addressed:

- a. Why are you doing this research project and what do you propose to learn?
- b. What is the justification for doing the study? Include, as appropriate, preliminary data and/or references to previous research, or gaps in our knowledge.

If you need more space, put "see attached" in the box and attach your complete purpose of study statement. Please title the attachment.

The current mental health crisis across college campuses particularly impacts students at Historically Black Colleges and Universities (HBCUs), who, compared to their Predominantly White Institution (PWI) counterparts, have fewer resources and less funding to support student psychological health [1]. While online therapy offers benefits, it does not solve the issue that the number of available therapists is insufficient to treat the number of students seeking help [2]. A promising solution is to increase opportunities for group therapy, which is equivalent to individual therapy in terms of outcomes [3]. As such, the purpose of our study is to assess the impact of an online, group text based therapy (one mental health counselor to many students) against a one-to-one (one mental health counselor to one student) therapy among HBCU students. Specifically, we will compare a HIPPA compliant, guided group telehealth (GGT) therapy (group therapy) called TheraGroup against a HIPPA compliant individual telehealth (IT) therapy (individual therapy) on measures of engagement, user experience, and mental health outcomes. If outcome measures in the GGT group are in line with outcome measures in the IT group, the feasibility study will serve as a precursor to testing the effects

RISKS AND BENEFITS

Describe any potential risks or discomforts to the participant (including physical, psychological and/or social):

Risks to subjects are rated as "Low", "Medium", "High". Do not say "none".

participants may be at risk of psychological harm. As the survey measures and therapy intervention ask participants to explore their mental health, specifically difficulties they may be having and traumatic events they have previously experienced, this process may exacerbate pre-existing mental health

Describe any potential benefits to the research participant or society:

Participants in this study will benefit from receiving mental health treatment from qualified professionals. Identifying effective group telehealth therapies to increase the access to mental health interventions contributes not only to the expansion of scientific knowledge within the field of mental health, but also to practical applications. Based on the findings of this study, interventions, trainings, and supports can be developed to treat mental illness in Black college students. This has potential

Describe alternatives to participation/opportunity to withdraw:

Participants may withdraw at any time

SUBJECT RECRUITMENT

Number of participants (target population): 8000 Ages of Participants: 18 years or older

Gender of subjects: Male

Maximum anticipated sample size: 200

Female

What are the selection criteria for participation (i.e. include target population and maximum anticipated sample size)?
For clarification on target population and maximum anticipated sample size, please refer to FAQ #35 on the [PVAMU IRB website](#).

Participants must be Black college students attending Prairie View A&M University (PVAMU) who are at least 18 years of age, and who qualify for psychological clinical intervention based on their current levels of depression and anxiety.

Do the criteria for selection exclude individuals based on gender, culture, language, economic status or ethnicity?

Yes No

If yes, please justify exclusion:

We are excluding non-Black individuals. The telehealth program we are testing is tailored for the Black population and thus we would like to test it on a matching sample.

Are there any special physical or psychological conditions of subjects? (If so, please describe.)

Participants who score a 5 or more on the GAD-7 (anxiety) or the PHQ-9 (depression) will qualify for the therapeutic intervention aspect of the study. These scores represent at least a minimal level of anxiety and depression.

Source of participants:

PVAMU students (provide explanation below) Community (provide explanation below)
 Schools* (provide explanation below) Other (provide explanation below)

Participants will be Black college students attending PVAMU

For studies involving schools:

Does the study involve a school district? Yes No

If Yes, which school district(s): _____

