Participants will access the study via an online link provided by email or via word of mouth. They will first answer a question to assess their suicide risk. If they have not had suicidal thoughts in the previous three weeks, they will continue on to the study. If they indicate they have had such thoughts in the prior three weeks, they will be disqualified from the study and a screen will appear with contact information regarding mental health resources. [name] will then reach out to Student Counseling Services and ask them to reach out to the students to follow-up and provide additional support. For those students who continue with the study, they will take the PHQ-9 and the GAD-7 to measure their depression and anxiety levels. If they score 5 or above on either test they will be invited to participate in the therapy part of the study. In this part of the study the participant will be assigned to either receive individual teletherapy or group teletherapy for 12 weeks. This therapy takes place via text. Participants may be asked to read psychoeducational materials and complete homework assignments. Participants assigned to the individual therapy, will receive support in the form of direct asynchronous communication with the therapist. Participants assigned to the group therapy will receive support in the form of direct asynchronous communication with the therapist and asynchronous communication with peers struggling with similar issues. Throughout the at week 4, 8 and 12 of therapy, participants will take the GAD-7, PHQ-9, and self-report questionnaires to measure their engagement and experience.

Describe the location where research activities will take place:

The research will take place on participants personal electronic devices by logging on to the web-based TheraGroup platform. TheraGroup is a proprietary real-time virtual based platform that provides text based group therapy. It is a cloud software that offers HIPAA compliant asynchronous text chat.

How long will the participants be engaged in research? (length of time, i.e. 15 minutes on day 1, etc.):

up to 12 weeks

During data collection, describe what steps will be taken to ensure participant privacy:

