“In the past few weeks, have you been thinking about killing yourself?”

If participant answers "yes" show the following resources:

- 24/7 National Suicide Prevention Lifeline [name] En Español:
[name]
- 24/7 Crisis Text Line: Text “HOME” to [name]
- PVAMU Student Counseling Services: [contact]
- 9-1-1

PRAIRIE VIEW A&M UNIVERSITY

A Member of the Texas A&M University System

To: **[name].**, Principal Investigator

From: **[name].**
IRB Chair

Date: October 28, 2024

Re: IRB Protocol #2024-044

The IRB protocol application submitted by you titled “Guided Group Telehealth to Deliver Evidence-Based Therapeutic Care to Black college students” has been deemed expedited and approved on October 28, 2024.

Any future correspondence regarding this study should reference the Protocol Title and Number. Please also make sure to use the consent forms with the “PVAMU Approved” Stamp.

A handwritten signature in black ink that reads "[name]".

[name].
IRB Chair
Office: [contact]

PLEASE NOTE: As the principal investigator of this study, you assume the following responsibilities:

- **Record Retention:** Records must be retained for at least 3 years after study completion.
- **Amendments:** Changes to research study activities may not be initiated without IRB approval.
- **Unanticipated Problems/Adverse events:** Any unanticipated problems/adverse events must be reported to the IRB immediately.
- **Informed Consent/Accent:** If applicable, all subjects must be given a copy of the stamped consent/assent document approved by the IRB (see attached).
- **Completion:** Once the study is complete, you must complete the [IRB-Completion-Report-Form.pdf \(pvamu.edu\)](#) and submit it to the Office of Research Compliance at [contact].

Prairie View A&M University
IRB Protocol Application

Received 7/8/2024

INSTRUCTIONS

1. Complete Training

PI, Co-Investigator and anyone interacting with potential participants must complete necessary training.

Refresher training must be completed every three years. More details can be found at: <http://www.pvamu.edu/research/office-of-research-compliance/207-revision-v1/irb-training/>

2. Complete Form

Form must be typed and free of typographical/grammatical errors.

3. Attach Documents to Application

- Recruitment materials as applicable: flyers, letters, scripts, e-mail, etc.
- Consent documentation as applicable: consent protocol, consent form or assent form
- Survey and/or Interview Questions

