Data will include the following: 1. Behavioral data (events that occur in the system due to students interacting with the system; e.g., time spent logged on) 2. Self-report data (measures of engagement, user experience surveys, the PHQ and GAD7 scores). Participant data will be collected via the TheraGroup systems backend in the form of log data (Behavioral Data) or through Qualtrics (Depression and Anxiety scores, measures of engagement, user experience surveys).

Will recordings be made?

- Yes
- No

If Yes:

- Video Taping
- Audio Taping
- Mandatory Recording
- Voluntary Recording

Is the use of recordings detailed in the consent form?

- Yes
- No

Will recordings be retained?

- Yes
- No

If Yes, how long will records be retained before they are destroyed/erased?

Will any new specimens be collected? (i.e. *blood tissue, etc.*)

- Yes
- No

If Yes, describe what specimens will be used and how they will be obtained:

Does the experiment involve the use of human fluid, tissue and/or blood?

- Yes
- No

Will any invasive or sensitive procedures be done?

Yes No

If Yes, check all that apply:

- Blood Samples
- Physical Measurements (electrodes, etc)
- rDNA
- Stress Exercise
- Urine Samples
- Other, specify: _____

DOCUMENT RETENTION

Federal regulations require that human research documents be retained for a minimum of three years AFTER the completion of the study AND data analysis. Some disciplines or granting agencies require longer retention times.

Length of time retained after completion of study and data analysis:

At least three years

Person responsible for data retention (*If you are a student, please list faculty mentor*) & data storage location:

All data will be kept on a password protected computer in [name] office in [name].

OTHER COMPLIANCE ISSUES

If the study involves the use of **animals, infectious biohazards (e.g. blood), and/or recombinant DNA**, it is required that approval be granted for the use of such through the appropriate compliance committee.

SIGNATURE ASSURANCES

PRINCIPAL INVESTIGATOR

I understand Prairie View A&M University's procedures concerning research involving human subjects and **by initialing** below, I certify:

AL I have read The Belmont Report "Ethical Principles and Guidelines for the Protection of Human Subjects of Research" and subscribe to the principles it contains.

AL I accept responsibility for the scientific and ethical conduct of this research study.

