7. Trouble concentrating on things, such as reading the newspaper or watching television
8. Moving or speaking so slowly that other people could have noticed. Or the opposite being so fidgety or restless that you have been moving around a lot more than usual
9. Thoughts that you would be better off dead, or of hurting yourself

GAD-7

Over the last two weeks, how often have you been bothered by the following problems?

Scale: 0 = not at all; 1 = several days; 2 = more than half the days; 3 = nearly every day

1. Feeling nervous, anxious, or on edge
2. Not being able to stop or control worrying
3. Worrying too much about different things
4. Trouble relaxing
5. Being so restless that it is hard to sit still
6. Becoming easily annoyed or irritable
7. Feeling afraid, as if something awful might happen

Engagement

On a scale from 1 to 5 with 1 being not at all to 5 being completely, rate how much the following statement applies to your experience with the telehealth therapy program:

1. I was interested in the therapy
2. I was intrigued when I used the telehealth therapy services
3. I was focused when I used the telehealth therapy services
4. I enjoyed using the telehealth therapy services

5. It was boring to use the telehealth therapy services
6. I felt frustrated using the telehealth therapy services
7. I found the telehealth services confusing
8. I felt unmotivated to use the telehealth services

User Feedback Experience

1. What, if anything, did you enjoy about your experience in using the guided telehealth therapy?
2. What, if anything, could be improved about your experience in using the guided telehealth therapy?
3. Did you feel the psychoeducational content was culturally relevant to you as a Black individual? Please explain

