Statistical Analysis Plan

Official Study Title: Guided group telehealth to deliver evidence-based therapeutic care to Black college students

NCT Number:

Date of Document: 03/10/2025

Statistical Analysis Plan

To test the primary hypothesis that participants in the Guided Group Telehealth (GGT) condition will experience reductions in depression and anxiety comparable to those in the Individual Telehealth (IT) condition, we will use a mixed-design repeated measures ANOVA. The within-subjects factor will be time (baseline, week 4, week 8, and week 12), and the between-subjects factor will be therapy condition (GGT vs. IT). The dependent variables will be PHQ-9 and GAD-7 scores, measuring depression and anxiety, respectively. Interaction effects will be examined to assess whether changes in symptom severity over time differ between the two conditions. For secondary analyses, we will use independent samples t-tests to compare user engagement and user experience scores between the two conditions at week 12. Descriptive statistics will be used to summarize engagement data, including participation rates, message frequency, and task completion. Additionally, qualitative analysis will be conducted on open-ended responses from the user experience survey to identify common themes related to participants' satisfaction and perceived effectiveness of the intervention. All analyses will be conducted using an alpha level of 0.05, and effect sizes will be reported alongside p-values. If violations of normality or sphericity are detected, appropriate corrections, such as Greenhouse-Geisser adjustments or nonparametric alternatives, will be applied.

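### Worsening of mental health is the one risk visible in the protocol, but the SAP compares only score averages between arms and has no by-arm summary of students who worsen or of reported adverse events

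*Protocol*

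**What the plan says.** **Risk.** The protocol's Risks and Benefits section says participants may suffer psychological harm, because the surveys and therapy ask about difficulties and past trauma and "this process may exacerbate pre-existing mental health". The box is cut off at that point. This is the only risk visible.

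**Reporting duty.** The IRB approval letter places a general duty on the principal investigator: "Any unanticipated problems/adverse events must be reported to the IRB immediately".

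**Data.** The Data Collection section lists two kinds of data. One is "Behavioral data (events that occur in the system due to students interacting with the system; e.g., time spent logged on"). The other is "Self-report data (measures of engagement, user experience surveys, the PHQ and GAD7 scores"). Adverse events and reasons for withdrawal are not listed, and the attached survey measures contain no item for either.

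**Schedule.** Under Procedures, at weeks 4, 8 and 12 "participants will take the GAD-7, PHQ-9, and self-report questionnaires to measure their engagement and experience". The PHQ-9 and GAD-7 are also taken at entry.

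**Suicidality.** The added suicide question is described only at entry. Students who answer yes do not go on to therapy: "they will be disqualified from the study and a screen will appear with contact information regarding mental health resources". PHQ-9 item 9, "Thoughts that you would be better off dead, or of hurting yourself", recurs with each PHQ-9, but no separate analysis of it is described.

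**Analysis.** The SAP uses a repeated measures ANOVA of PHQ-9 and GAD-7 by arm and time: "Interaction effects will be examined to assess whether changes in symptom severity over time differ between the two conditions". Engagement and experience are compared by t-tests at week 12, engagement is also described, and open-ended answers are analysed for themes. The SAP has no harm outcome.

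**Use of the result.** The Purpose of Study section says that if group outcomes match individual outcomes, this feasibility study leads on to further testing. No condition on harm is attached.

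**The concern.** The foreseen harm happens to individual students, while the planned comparison is of averages. A minority who deteriorate can be offset by others who improve more, so two arms can show the same mean trajectory with different numbers of students worse off than at baseline. Followed as written, the SAP could support a statement that group therapy is comparable without anyone having tabulated deterioration by arm.

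Timing matters too. A definition of worsening is credible only if it is fixed before the data are reviewed. Adverse events and withdrawal reasons that are not recorded during the study may not be recoverable afterwards.

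**Working it through.** The documents give no figure to reproduce. The 200 under Subject Recruitment is a maximum, and no standard deviation, margin, dropout rate or expected rate of worsening is stated. The check is therefore a comparison of sections followed by an illustration on assumed values.

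**Step 1: named harm against data and analysis**

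| Needed to see the harm by arm | Where it stands |
|---|---|
| Baseline and follow-up scores | Collected at entry and weeks 4, 8 and 12 |
| Definition of worsening | Absent from the SAP |
| Count of worsened students by arm | Absent from the SAP |
| Adverse events | Reporting duty in the IRB letter; not in the Data Collection list; no SAP summary |
| Reasons for withdrawal | Not in the Data Collection list; no SAP summary |

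The gap is thus mainly one of analysis, with a smaller gap in recording.

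**Step 2: can equal means hide unequal worsening?**

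Assumptions: change from baseline is normal with the same mean m in both arms, and worsening means a rise of 5 points or more. The standard deviation (SD) of change is 5 in individual therapy (IT) and 5, 6 or 7 in group therapy (GGT).

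Formula: P(worsen) = 1 − Φ((5 − m)/SD).

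For m = −4:

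- SD 5: (5 + 4)/5 = 1.80, giving 3.6%
- SD 6: 9/6 = 1.50, giving 6.7%
- SD 7: 9/7 = 1.29, giving 9.9%

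| Mean change, both arms | IT, SD 5 | GGT, SD 5 | GGT, SD 6 | GGT, SD 7 |
|---|---|---|---|---|
| −3 | 5.5% | 5.5% | 9.1% | 12.7% |
| −4 | 3.6% | 3.6% | 6.7% | 9.9% |
| −5 | 2.3% | 2.3% | 4.8% | 7.7% |

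With equal mean change, the arm-by-time interaction has no true difference to detect. With equal spread as well, the arms do not differ in worsening, so the masking depends on the assumed difference in spread.

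**Step 3: how much would a by-arm count tell us?**

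Assume 100 per arm (200 split equally; the allocation ratio is not stated). The approximate 95% half-width for the difference is 1.96 × √(p₁(1 − p₁)/n + p₂(1 − p₂)/n).

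- 5% v 10%: 1.96 × √(0.000475 + 0.0009) = 0.073
- 10% v 20%: 1.96 × √(0.0009 + 0.0016) = 0.098

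So the interval reaches about 7 to 10 percentage points either side. With 80 per arm the same cases give 0.081 and 0.110. Two-sided power at 0.05 with 100 per arm is 0.27 for 5% v 10% and 0.66 for 5% v 15%. Reaching 80% power would need 435 and 141 per arm. The count is useful as description only.

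**Step 4: which definition of worsening?**

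A count of any rise on either scale at any of three visits gives 2 × 3 = 6 chances to cross the line. Take a threshold of 6 points, mean change −4, SD 5 and a correlation of 0.5 to 0.7 among the six changes (all assumed). At one assessment, 1 − Φ((6 + 4)/5) = 1 − Φ(2) = 2.3% cross; over six, about 8 to 10% cross at least once. Students with fewer completed visits also have fewer chances. One time point per scale avoids both problems.

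**The case against.** **The trial does deal with adverse events.** A reader might infer that none are captured. The documents do not support that: the IRB letter requires them to be reported immediately. What stands is narrower. The visible text does not define them, actively elicit them, list them as study data or summarise them by arm.

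**The text is incomplete.** A reader might call worsening the main risk, or conclude that therapists have no route for passing events to the principal investigator. Neither can be asserted. The risk box is cut off, no rating is visible, and consent and other pages were removed, so a harm procedure may exist there. The SAP itself gives no analysis of harm.

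**Related information is collected.** The engagement scale asks about frustration, confusion and motivation, an open question asks what could be improved, and participation rates are reported. These may hint at trouble, but they do not measure a rise in depression or anxiety.

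**Comparability is loosely defined anyway.** The SAP gives no margin and relies on an interaction test, so a claim of comparability is easy to reach for reasons unrelated to harm. That is a separate weakness and is not counted here.

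**Counting will not settle it.** A reader might infer that a count of worsened students would detect what the means miss. Step 3 of the working shows that it often would not at this size. This objection stands in full and shapes the fix.

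**It is a feasibility study.** That argues against a powered safety test. It does not argue against one descriptive table, since the study's result feeds a decision on further testing.

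**Conclusion.** The concern holds in limited form. The SAP has no by-arm summary of individual worsening or of reported adverse events, and the visible Data Collection text lists neither adverse events nor reasons for withdrawal. The planned comparison of means cannot by itself show the harm the protocol names.

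The size is illustrative. With equal mean change of −4 points and standard deviations of 5 v 7, worsening is 3.6% v 9.9%, a difference of 6.3 percentage points. Across mean changes of −3 to −5 with the same spreads, the difference runs from 7.2 (5.5% v 12.7%) down to 5.4 (2.3% v 7.7%). The normal distribution, the spreads and the 5-point threshold are all assumptions. One counselor serving many students makes greater spread in the group arm conceivable, but nothing in the documents establishes it. They give no evidence that group therapy harms more students.

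This should be corrected because the fix is cheap. It does not invalidate the trial.

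**What to change.** 1. **SAP: one descriptive table by arm.** For PHQ-9 and GAD-7 separately, give the number and percentage of students whose score rose from baseline to week 12 by an amount fixed before data review. Week 12 is the primary time point for this table, with weeks 4 and 8 as supporting rows. Give the arm difference with a Newcombe or other score-based 95% interval, since counts may be small. Show the number with missing scores by arm, because students who worsen may leave and a standard repeated measures ANOVA uses complete cases.
2. **Protocol, Data Collection: two short records.** Add an adverse-event entry and a reason-for-withdrawal item, both tabulated by arm in the SAP.
3. **Reporting.** Require any statement that the arms are comparable to appear alongside this table. Do not make it conditional on a test of the table, which would be underpowered.

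**Cost.** A paragraph of SAP text, one table, a brief event entry and one extra item. The protocol change needs IRB approval under the terms of the approval letter. No new score collection is needed and no treatment rule changes. The drawback is imprecision: with intervals of about 7 to 10 percentage points either side at an assumed 100 per arm, the table must be labelled descriptive, and a result showing little difference must not be read as proof of equal safety.
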